6.3. Efficacy Analysis

All efficacy endpoints will be summarized by substudy and cohort. P-values and 95% CIs will be provided where appropriate. Comparisons between cohorts of substudy 4 will be performed using descriptive statistics and for the purposes of hypothesis generation only.

All efficacy analyses will be conducted using the mITT population. To evaluate sensitivity, the primary efficacy analyses (i.e. Section 6.3.1), will also be conducted using the PP population.

Assessments by Blinded Independent Central Review (BICR) consider two readers. Should there be disagreement between these two readers, an adjudicator decides which reader is correct. As such, all analyses which consider BICR assessments will be based upon the first reader by default, unless the second reader is selected following adjudication.

Per protocol inclusion criteria, only patients with measurable disease by RECIST version 1.1 criteria should be enrolled. If a patient without measurable disease is enrolled, the ITT principle requires including these patients in the analyses. Hence, analyses will be based on patients with either measurable or non-

measurable disease. For this purpose, non-CR/non-PD in patients with non-measurable disease will be considered equivalent to SD in patients with measurable disease, and the same rules will be applied.

Waterfall plots, spider plots and swimmer plots will be produced to accompany efficacy analyses.

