3.1.7 Survival Follow-up period

Patients who are permanently discontinued from study treatment for reasons other than death and consent withdrawal for further safety and survival follow-up, regardless of the reason, will enter the survival follow-up period (see Section 5.2.3).

Survival Follow-up (at least every 3 months \pm 14 days from last dose of study drug) will start on the day of the last dose of either study drug and will continue until the study has completed (see Section 3.1.8) or other discontinuation criteria are met (see Section 4.4.4).

All subsequent anticancer therapies should continue to be recorded on the appropriate electronic case report form (eCRF) for the duration of the patient's survival follow up.

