8.2.2 Modified intent-to-treat population

For all efficacy endpoint analyses, a mITT population will be used, comprising all patients who received at least one dose of derazantinib or atezolizumab, and have at least one post-baseline imaging assessment in accordance with RECIST 1.1, or documented clinical

progression (every effort should be made to objectively assess radiographic progression). Non-evaluable patients will be replaced.

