8.3.4.2 Secondary efficacy endpoints

DCR will be summarized in the same way as the primary endpoint.

DOR, PFS and OS analyses will be performed using KM methods. The analysis will be performed on the mITT population and repeated on the PP population.

DoR will be calculated from the first date of documented tumor response (CR or PR) to the date of disease progression by BICR. If a patient is discontinued or is lost to follow-up with no documentation of PD, duration of response is defined as the time from the date of the first documentation of objective response to the date of the last tumor assessment as a censored value. If the patient dies with no documentation of PD, duration of response is defined as the time from the date of the first documentation of objective response to the

date of the last tumor assessment as a censored value. Patients who crossover to derazantinib-atezolizumab combination will be censored at time of crossover.

PFS will be calculated as the time from cohort assignment by IWRS until disease progression per RECIST 1.1, or death from any cause. Patients who discontinue treatment due to reasons other than disease progression by BICR or death will be censored in the PFS analyses at the date of their last tumor evaluation. Patients who progress or die after missing ≥ 2 consecutive scheduled tumor assessments will be censored at the date of the last tumor evaluation prior to progression or death. Patients who either have no baseline tumor evaluation or have no post baseline tumor evaluation will be censored at the date of the first dose. Patients who crossover to derazantinib-atezolizumab combination will be censored for the derazantinib analysis at the time of crossover. For patients crossing over from derazantinib to derazantinib-atezolizumab in combination and as an exploratory analysis, hazard ratios (HRs) for median OS time will be calculated using an Inverse Probability of Censoring Weighted (IPCW) modeling approach ([Rimawi 2012](#)).

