5.2. Modified Intent-to-treat (mITT) Population

For all efficacy endpoint analyses, a mITT population will be used, comprising all patients who received at least one dose of derazantinib or atezolizumab, and have at least one post-baseline imaging assessment in accordance with RECIST 1.1, or documented clinical progression (every effort should be made to objectively assess radiographic progression) or death. Non-evaluable patients will be replaced.

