5.3. Per-protocol (PP) Population

The PP population will include all patients in the mITT population who have no major protocol deviations which are determined to potentially impact efficacy analyses during the study. Protocol deviations will be identified prior to final analysis.

This analysis population will be used for secondary analysis of primary and secondary endpoints.

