6.3.2.4. Overall Survival (All Substudies)

Overall Survival (OS) will be calculated from the date of cohort assignment by IWRS until death from any cause. Any patient without a date of death in the database at the time the survival analyses are performed will be censored at the time of their last study contact. Crossover patients (Cohort 4a) will be censored at the time of crossover in the primary analysis of OS.

OS will be analyzed using Kaplan-Meier methodology ([Kaplan & Meier 1958](#)). The median duration of OS will be presented along with the standard error and 2-sided 95% CI. If they are calculable, the 25th and 75th percentiles and the 2-sided 95% CIs around the percentiles will be presented. Kaplan-Meier estimates at 3, 6, 9 and 12 months will also be presented. The Kaplan-Meier survival curves will also be presented. For substudy 4 comparisons between cohorts will be made by considering a hazard ratio, with associated 2-sided 95% confidence interval and p-value, from an unadjusted Cox proportional hazards model.

These analyses will be performed per cohort in substudies 1, 3, 4 and 5 and by dose level in substudy 2. The date of cohort assignment by IWRS, first dose, death, last study contact and OS days will be reported in a by-patient listing.

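### The SAP's survival analysis set keeps a dosed patient with no scan and no documented clinical progression if he dies and drops him if he lives, so inclusion in OS depends on the OS event

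*SAP*

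**What the plan says.** - **Population for OS.** SAP 6.3: "All efficacy analyses will be conducted using the mITT population". SAP 6.3.2.4 (Overall Survival) names no other set. Protocol 8.3.4.2 says of DOR, PFS and OS: "The analysis will be performed on the mITT population and repeated on the PP population".
- **Who is in mITT under the SAP.** SAP 5.2 describes the set as "comprising all patients who received at least one dose of derazantinib or atezolizumab, and have at least one post-baseline imaging assessment". Documented clinical progression is an alternative to the scan. The sentence then ends: "every effort should be made to objectively assess radiographic progression) or death. Non-evaluable patients will be replaced". The death carries no time limit.
- **Who is in mITT under the protocol.** Protocol 8.2.2 has the scan and clinical progression routes but no death route: "progression (every effort should be made to objectively assess radiographic progression). Non-evaluable patients will be replaced".
- **Censoring.** SAP 6.3.2.4: "Any patient without a date of death in the database at the time the survival analyses are performed will be censored", at last study contact.
- **Follow-up.** Under Protocol 3.1.7, patients who stop treatment, other than through death or withdrawal of consent to follow-up, "regardless of the reason, will enter the survival follow-up period".
- **Per-protocol set.** SAP 5.3: "The PP population will include all patients in the mITT population who have no major protocol deviations".
- **Declared changes.** SAP 6.8 lists only the dropped IPCW model.

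**The concern.** Survival needs no tumour scan, and vital status is collected for treated patients whether or not they were imaged. Tying the OS set to imaging is therefore unnecessary. With death as one of the entry routes it also makes membership depend on the endpoint. Among patients who have neither a scan nor documented clinical progression, every death counts and none of the censored survival time does.

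The set is also unstable. Protocol 8.3.4.2 allows OS to be repeated when long-term data are available. A patient left out as alive at one cut joins as an event at a later cut if he has died, possibly after he has been replaced.

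At stake are the OS median and the 6-month OS rate, which are named secondary endpoints, the Kaplan-Meier estimates at 3, 6, 9 and 12 months, and the Substudy 4 hazard ratio for OS, which rests on the same set.

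**Working it through.** **Step 1: membership.** Take dosed patients with no post-baseline scan and no documented clinical progression.

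| Status at cut-off | SAP 5.2 mITT | Protocol 8.2.2 mITT | All dosed (safety/ITT) |
|---|---|---|---|
| Dead | in, event | out | in, event |
| Alive | out | out | in, censored at last contact |

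Patients with a scan or documented clinical progression are in all three sets. The per-protocol set is nested in mITT, so repeating the analysis there restores nobody. The SAP 6.3.1 rule that patients without efficacy assessments count as non-responders concerns response and does not define the OS set.

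**Step 2: size.** The plan has no OS figure to reproduce. These inputs are assumptions: exponential survival with median 9 months, so λ = ln 2 / 9 = 0.0770 per month; follow-up C uniform on 6.2 to 18.2 months; a fraction f of dosed patients with neither scan nor clinical progression, having the same survival as the rest.

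Probability of being alive at cut-off: (e^(−6.2λ) − e^(−18.2λ)) / (12λ) = (0.6203 − 0.2462) / 0.9242 = 0.405. With f = 10%, 0.10 × 0.405 = 4.05% of dosed patients are dropped, all of them alive. That is about 1 patient in 26 or 3 in 74.

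With S the true survival function and G(t) = P(C > t), the hazard seen in the SAP set is

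h(t) = λ S(t) G(t) / [(1 − f) S(t) G(t) + f D(t)], where D(t) = ∫ from t to 18.2 of λ S(u) G(u) du.

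For f = 10%:
- t = 0: D = 1 − 0.405 = 0.595, so the hazard is inflated by 1 / (0.9 + 0.1 × 0.595) = 1.042.
- t = 6.2: S G = 0.6203 and D = 0.6203 − 0.4048 = 0.2155, so the inflation is 0.6203 / (0.9 × 0.6203 + 0.1 × 0.2155) = 1.070.

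Integrating h(t) numerically:

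| f | Dropped alive | Median, all dosed | Median, SAP set | 6-month OS, all dosed | 6-month OS, SAP set |
|---|---|---|---|---|---|
| 2% | 0.8% | 9.00 | 8.90 | 0.630 | 0.627 |
| 5% | 2.0% | 9.00 | 8.75 | 0.630 | 0.622 |
| 10% | 4.05% | 9.00 | 8.49 | 0.630 | 0.614 |
| 15% | 6.1% | 9.00 | 8.25 | 0.630 | 0.606 |

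**Step 3: sensitivity, f = 10%.**
- Follow-up 18 to 30 months: SAP-set median 8.79. Follow-up 24 to 36 months: 8.87.
- No-scan patients with median survival 3 months: 8.04 for all dosed against 7.95 in the SAP set (follow-up 6.2 to 18.2 months).
- The same early deaths, but no-scan patients lost to contact at 0.5 to 6 months (other patients followed 6 to 24 months): 8.47 against 8.28.

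**Step 4: the protocol's definition.** It drops these patients dead or alive. With equal survival this leaves OS unbiased. If they die early, it biases OS upward. With f = 10%, a 3-month median in the no-scan patients and follow-up of 6 to 24 months, simulation gives 8.98 months in that set against 8.02 for all dosed. This shows direction only.

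**The case against.** - **End-of-Treatment imaging should catch most of these patients.** Protocol 5.2.2.7 and footnote 13 of Table 1 call for a scan at End of Treatment if there was none in the preceding 28 days or the prior scan showed no progression. Protocol 5.3.3.2.3 asks for every effort at imaging when progression is undocumented. This stands. A reader might infer that anyone who stops for toxicity before week 9 is affected, but such a patient is normally due a scan that puts him in mITT, alive or dead. Only those who also miss that scan are affected. The replacement rule in Protocol 4.5.3 shows that the plan expects some non-evaluable patients, but no rate is given.
- **Clinical progression is another way in.** A reader might infer that every unscanned survivor is dropped. SAP 5.2 does not support that, because documented clinical progression keeps him.
- **The death criterion may have been meant for early deaths only.** That is plausible, but the text sets no limit.
- **The protocol's definition could suggest a large upward bias.** Protocol section 8 leaves analysis details to the SAP, and the SAP's death route restores those deaths. Any upward figure also needs an assumed share of early deaths without documented clinical progression, which the documents do not give.
- **The effect is small against the available precision.** With a true median of 9 months and the same follow-up, the simulated 95% range of the estimated median is about 4.6 to 14.6 months for 26 patients and 6.4 to 12.8 for 74. This stands.
- **Nothing turns on it.** OS enters no stage or rejection rule, Substudy 4 comparisons are hypothesis-generating, the SAP-side bias is conservative, and exclusions are listed by patient. This stands and limits the weight of the point, but it does not justify selecting patients on the outcome.

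**Conclusion.** The point holds in a limited form. Followed as written, the SAP selects part of its OS set on the OS event. The defect is confined to dosed patients with neither a post-baseline scan nor documented clinical progression. It biases OS downward and lets membership change between data cuts. The protocol's set errs differently, and the change between the two definitions is not declared in SAP 6.8.

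Under the stated assumptions (true median 9 months, equal survival, follow-up of about 6 to 18 months, 2 to 15% such patients) the median is about 0.1 to 0.8 month low and 6-month OS about 0.3 to 2.4 percentage points low. The shift is usually smaller if these patients die early or follow-up is longer. Neither the no-scan rate nor the survival assumption comes from the documents.

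A reader might go further and infer that the OS results will not describe treated patients at all. The documents do not support that: the affected group may be very small, and the primary ORR decisions are untouched. It is a defect worth correcting in a named secondary endpoint.

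**What to change.** - In SAP 6.3 and 6.3.2.4, and in Protocol 8.3.4.2, state that OS is analysed on all patients who received at least one dose (the safety/ITT set), with patients alive censored at last contact.
- Keep OS on mITT as a supportive table if wanted.
- List the death criterion added to mITT in SAP 6.8.

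The cost is one sentence, a different population flag on the OS outputs and one line in SAP 6.8. No new data are needed, because survival follow-up already covers these patients. The OS denominator may differ slightly from the ORR denominator, which a table footnote can explain.

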6.3.1. Primary Efficacy Analysis

6.3.1.1. Objective Response Rate

The primary efficacy endpoint in all substudies will be objective response rate (ORR), defined as the achievement of confirmed CR or PR using RECIST 1.1 ([Eisenhauer 2009](#)) as assessed by BICR. Point estimates and exact 2-sided 95% CIs will be provided.

Classification of best confirmed response is done according to the following hierarchy and rules:

1. Complete Response (CR): requires two consecutive CR response assessments a minimum of four weeks apart
2. Partial Response (PR): requires two consecutive PR response assessments OR a PR response immediately followed by a CR response assessment (a minimum of four weeks apart)
3. Stable Disease (SD): requires only one SD response assessment (provided minimum criteria for SD duration met)
4. Non-CR/Non-PD (non-measurable disease patients only): requires only one Non-CR/Non-PD response assessment (provided minimum criteria for Non-CR/Non-PD duration met)
5. Progressive Disease (PD): requires only one PD response assessment

The minimum duration for SD and Non-CR/Non-PD is defined as 6 weeks, where the duration is calculated from the start of treatment until the criteria of SD is met.

The classification as per RECIST 1.1 ([Eisenhauer 2009](#)) is summarized in Table 4.

Table 4: Best overall response when confirmation of CR and PR required.

Overall response		BEST overall response
First time point	Subsequent time point	
CR	CR	CR
CR	PR	SD, PD or PR*
CR	SD	SD provided minimum criteria for SD duration met, otherwise PD
CR	PD	SD provided minimum criteria for SD duration met, otherwise PD
CR	NE	SD provided minimum criteria for SD duration met, otherwise NE
PR	CR	PR
PR	PR	PR
PR	SD	SD
PR	PD	SD provided minimum criteria for SD duration met, otherwise PD
PR	NE	SD provided minimum criteria for SD duration met, otherwise NE
NE	NE	NE

CR = complete response, PR = partial response, SD = stable disease, PD = progressive disease, and NE = inevaluable.
 * If a CR is truly met at first time point, then any disease seen at a subsequent time point, even disease meeting PR criteria relative to baseline, makes the disease PD at that point (since disease must have reappeared after CR). Best response would depend on whether minimum duration for SD was met. However, sometimes 'CR' may be claimed when subsequent scans suggest small lesions were likely still present and in fact the patient had PR, not CR at the first time point. Under these circumstances, the original CR should be changed to PR and the best response is PR.

As specified in RECIST 1.1, repeated 'NE' time point assessments complicate best response determination. Should a CR/PR be followed by a NE response and then a CR/PR, then confirmed response would be achieved (as an example PR-NE-PR will be considered as a confirmed response).

Note that iRECIST criteria (an adaptation of RECIST 1.1 to account for the tumor response patterns seen with immunotherapeutic drugs ([Seymour 2017](#))) will also be considered in exploratory analyses.

Patients without efficacy assessments are considered non-responders, and included in the analysis.

Hypothesis testing (null hypothesis [H₀] versus alternative hypothesis [H_A]) will be performed at the interim and final analyses as specified below:

Substudy 1

H₀: p ≤ 0.21 versus H_A: p ≥ 0.34

If there are seven or fewer patients with an objective response (defined as a confirmed CR or PR) in the first 35 evaluable patients included in the interim analysis, the substudy will be stopped. If not, an additional 39 patients will be enrolled, for a total of 74 evaluable patients. The null hypothesis will be rejected if 22 or more objective responses are observed in these 74 patients.

Substudy 3

H₀: p ≤ 0.25 versus H_A: p ≥ 0.45

If there are four or fewer patients with an objective response (defined as a confirmed CR or PR) in the first 18 evaluable patients included in the interim analysis, the cohort will be stopped. If not, an additional 18 patients will be enrolled, for a total of 36 evaluable patients. The null hypothesis will be rejected if 14 or more objective responses are observed in these 36 patients (or if 10 or more responses are observed in

the first 18 patients). Posterior estimates of the probability that the response rate exceeds 0.25 will also be calculated assuming a non-informative prior distribution. A prior distribution Beta(1,1) will be used as a vague, non-informative prior, giving a uniform distribution with mean of 0.5 response rate with wide uncertainty. This will be multiplied by a likelihood with distribution Beta(a,b) where a is the number of responses and b is the number of non-responses, to obtain the posterior distribution from which the probability that the response rate exceeds 0.25 will be estimated. This analysis will only consider BICR assessed response within the mITT population.

Substudy 4

$H_0: p \leq 0.07$ versus $H_A: p \geq 0.20$

If there are one or zero patients with an objective response (defined as a confirmed CR or PR) in the first 16 evaluable patients included in the interim analysis in each of Cohort 4a and 4b, the cohort will be stopped. If not, an additional 34 patients will be enrolled, for a total of 50 evaluable patients. The null hypothesis will be rejected if 7 or more objective responses are observed in these 50 patients.

Comparisons between cohorts will be descriptively summarized by reporting the difference in point estimates between cohorts, with a 2-sided exact 95% CI for the difference and a p-value from a Fisher exact test.

Substudy 5

$H_0: p \leq 0.10$ versus $H_A: p \geq 0.30$

If there is one or fewer patient with a response (defined as a CR or PR) in the first 13 evaluable patients included in the interim analysis, the cohort will be stopped. If not, an additional 13 patients will be enrolled, for a total of 26 evaluable patients. The null hypothesis will be rejected if six or more responses are observed in these 26 patients (or if five or more responses are observed in the first 13 patients). Posterior estimates of the probability that the response rate exceeds 0.1 will also be calculated assuming a non-informative prior distribution. This analysis will only consider BICR assessed response within the mITT population.

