8 STATISTICAL CONSIDERATIONS AND ANALYTICAL PLAN

Effective Protocol Version 5.0, only statistical considerations applicable to active substudies are provided in this section.

Details of the statistical analyses presented below will be provided in the study's statistical analysis plan (SAP). A change to the data analysis methods described in the protocol will require a protocol amendment only if it alters a principal feature of the protocol. The SAP will be finalized prior to database lock. Any changes to the methods described in the plan will be described and justified in the final clinical study report.

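### Substudy 3: the SAP's posterior formula, read literally, gives Beta(a,b) rather than the Beta(1+a,1+b) implied by its stated uniform prior

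*SAP*

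**What the plan says.** SAP Section 6.3.1.1 sets out a supplementary Bayesian summary for Substudy 3. The prior is explicit: "A prior distribution Beta(1,1) will be used as a vague, non-informative prior, giving a uniform distribution with mean of 0.5 response rate". The next sentence gives the updating step: "This will be multiplied by a likelihood with distribution Beta(a,b) where a is the number of responses and b is the number of non-responses". The product is used "to obtain the posterior distribution from which the probability that the response rate exceeds 0.25 will be estimated". The response data for this summary are also fixed: "This analysis will only consider BICR assessed response within the mITT population".

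The parameters of the resulting posterior are not written out. Protocol Section 8.3.4.1 commits to the same summary but says only that the prior is non-informative. Protocol Section 8 defers further specification, stating: "Details of the statistical analyses presented below will be provided in the" SAP. Within the two documents, the SAP sentence is therefore the only statement of the calculation.

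The decision rules in the same SAP section are separate and use counts. The cohort stops with "four or fewer patients with an objective response (defined as a confirmed CR or PR) in the first 18 evaluable patients". At the end, "The null hypothesis will be rejected if 14 or more objective responses are observed in these 36 patients", or earlier with at least 10 responders among the first 18.

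For Substudy 5 the SAP says: "Posterior estimates of the probability that the response rate exceeds 0.1 will also be calculated assuming a non-informative prior distribution". It gives no distribution, parameters or formula there.

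**The concern.** The passage writes Beta(1,1) and Beta(a,b) in the same notation and defines a and b as raw counts. If both are read as densities and multiplied, the flat prior contributes nothing and the posterior is Beta(a,b). That does not follow from the uniform prior named one sentence earlier.

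Two programmers could each claim to follow the text and obtain different values, one by multiplying the named densities and the other by adding the counts to the prior parameters. What is at stake is whether a prespecified output in the primary efficacy section matches its own stated prior.

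**Working it through.** **Inputs** (SAP Sections 6.1.6.3 and 6.3.1.1): prior Beta(1,1); a responses and b = n − a non-responses; threshold 0.25; Stage 1 n = 18, stop at 4 or fewer, reject at 10 or more; final n = 36, reject at 14 or more.

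**1. The plan's own design figures.** The SAP states type I error 0.046, power 81%, and average sample size 27 under H0 and 31 under the alternative. With X1 and X2 independent Binomial(18, p):

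- P(reject) = P(X1 ≥ 10) + Σ over x = 5 to 9 of P(X1 = x)·P(X2 ≥ 14 − x). This is 0.0462 at p = 0.25 and 0.8098 at p = 0.45.
- Average N = 18 + 18·P(5 ≤ X1 ≤ 9). This is 26.6 at p = 0.25 and 30.7 at p = 0.45.

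These reproduce. The documents give no numerical posterior to reproduce.

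**2. The algebra.**

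- Literal text: the Beta(1,1) density is 1 and the Beta(a,b) density is proportional to p^(a−1)(1−p)^(b−1). The product is Beta(a,b), with mean a/n. This is the posterior under an improper Beta(0,0) prior and is undefined when a = 0.
- Stated prior with binomial data: 1 × p^a(1−p)^b, which is Beta(1+a,1+b), with mean (a+1)/(n+2).

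At 14/36 the means are 14/36 = 0.389 and 15/38 = 0.395.

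**3. Check by numerical integration at 14/36.** The Beta(1,1) density times the Beta(14,22) density, normalised, gives P(p > 0.25) = 0.9637. The Beta(1,1) density times the Binomial(36, p) likelihood at 14, normalised, gives 0.9728. These match the closed forms.

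**4. P(ORR > 0.25) under the two readings.**

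| Responses | Stated uniform prior, Beta(1+a,1+b) | Literal text, Beta(a,b) | Gap |
|---|---|---|---|
| 4/18 (stops) | 0.465 | 0.353 | 0.112 |
| 5/18 (lowest count that continues) | 0.668 | 0.574 | 0.094 |
| 10/18 (early rejection) | 0.998 | 0.997 | 0.001 |
| 8/36 | 0.400 | 0.322 | 0.077 |
| 9/36 (observed 25%) | 0.550 | 0.474 | 0.076 |
| 10/36 | 0.691 | 0.626 | 0.065 |
| 13/36 | 0.942 | 0.924 | 0.018 |
| 14/36 (rejection boundary) | 0.973 | 0.964 | 0.009 |

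The largest gaps are at 4/18 and 8/36.

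**5. Direction of the error.** The beta recurrences give, with x = 0.25,

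P(Beta(1+a,1+b) > x) − P(Beta(a,b) > x) = [x^a(1−x)^b / B(a,b)] × (b − xn)/(ab).

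This is positive whenever b > 0.25n, that is, whenever fewer than 75% of patients respond. The literal reading is therefore too low at every count from 1 to 10 of 18 and from 5 to 16 of 36.

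**6. Zero responses.** At a true ORR of 25%, the chance of 0/18 is 0.75^18 = 0.006. The undefined case is possible but unlikely.

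**The case against.** The strongest reply is that this is loose notation. The sentence calls the object a likelihood and defines a and b as counts. The likelihood of those counts is p^a(1−p)^b whatever label is attached, and with the uniform prior just named that gives Beta(1+a,1+b). A reader who updates conjugately gets the intended answer. No posterior value is printed anywhere, so no reported figure is wrong. The table shells are in a separate document (SAP Section 7.2) and might state the posterior.

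On impact, no threshold attaches to this probability, and 0.5 is not a cut-off in the plan. The largest gap falls at 4/18, where the cohort already stops. At or above the efficacy boundaries the gap is at most 0.009 at 36 patients and 0.001 at 18. The literal value is the lower one over the relevant range, so it would not inflate an efficacy claim.

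The points on impact all stand and keep this minor. The inferred intent also stands. It does not make the written formula correct: a Beta(a,b) with raw counts is not the likelihood shape, which is Beta(a+1,b+1). The sentence specifies a calculation to be programmed. The Substudy 5 text contains no formula, so it does not share this error and adds no weight to it.

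**Conclusion.** The concern holds, at minor severity. Read literally, the SAP's updating step gives Beta(a,b), which contradicts the uniform prior stated immediately before it. The reported P(ORR > 0.25) would be too low by 0.009 at the final rejection boundary, 0.076 at an observed 25% of 36, and 0.094 at the lowest count that continues past Stage 1.

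This rests on reading Beta(a,b) as a density with the parameters the SAP gives it. If it is taken as shorthand for the binomial kernel, the result is right and only the wording is wrong. The stop and reject rules, type I error, power and average sample size are unaffected under either reading.

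**What to change.** Replace the updating sentence in SAP Section 6.3.1.1 (Substudy 3) with: *With a responses and b non-responses, the binomial likelihood and the Beta(1,1) prior give a Beta(1+a, 1+b) posterior, from which P(ORR > 0.25) is computed.* This keeps the SAP's own prior.

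As a clarification only, add a cross-reference in the Substudy 5 paragraph to the same prior and posterior, with threshold 0.10.

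The cost is one sentence replaced and one cross-reference added in the SAP. No design element or decision rule changes.
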